### **7.2.5 Sponsor Responsibility for Reporting Adverse Events**

All Adverse Events will be reported to regulatory authorities, IRB/IECs and investigators in accordance with all applicable global laws and regulations.

## **8.0 STATISTICAL ANALYSIS PLAN**

### **8.1 Statistical Analysis Plan Summary**

This is a single arm phase IIa clinical trial, conducted in 2 independent patient groups, consisting of (a) non-small cell lung and (b) head and neck squamous cell carcinoma patients, intended to determine the safety of the combination as well overall response rate, together with the impact of the two drug combination on T cell and NK cell trafficking into the tumor.

### **8.2 Statistical Analysis Plan and Sample Size Determination**

Determination of overall response rate will be calculated based on the evaluable population of patients who received at least 1 dose of therapy. Best overall response at any time will be compared in the study population to benchmark values in the literature. Overall and progression free survival will be determined according to the method of Kaplan and Meier and analyzed for each cohort. For the endpoints of ORR, OS and PFS, each of these will be analyzed in groupings of patients according to biomarkers of interest including (a) PD-L1 expression on archival tissue and current peripheral blood CTCs, (b) peripheral blood T cell subset analysis, (c) quantitative T-cell tumor infiltration, and (d) genomic complexity and (e) integrin expression pattern in tumor blood vessels. The impact of treatment on the levels of PD-L1 expression, T-cell subsets and Tumor infiltrating lymphocytes will be compared in archival and post treatment biopsy specimens. Adverse events will be tabulated for the duration of the trial and reported in tabular format.

Sample size is determined independently for each of the 2 patient groups, and is based on overall response rate using a Simon Optimal 2-stage design.

$$H_0: \pi < 20\%$$

$$H_a: \pi > 45\%$$

where  $\pi$  = the true response rate (same rate used for NSCLC and H&N Cancer)

For the type 1 and type 2 error probability,  $\alpha=\beta=0.10$ , up to 25 patients are required in each arm to have sufficient power to test the hypothesis. Interim response rate will be determined after 14 patients have been enrolled on each arm. If there are fewer than 3 responses in the first 14 patients, the alternate hypothesis will be rejected and that arm of the study will be closed. If 4 or more responses occur, then accrual will continue on that arm until 25 patients have been treated and evaluated. If 8 or more of the 25 patients experience an objective response, then we will conclude that the true response rate is clearly greater than 20% and not incompatible with a response rate of 45% - and this will serve as a signal indicating that the

two drugs together are better than either alone. However, if 7 or fewer patients experience a response, then we will conclude that the true response rate is less than 45% and not incompatible with a response rate of 20%.

Once 14 patients in each cohort have been enrolled, accrual to the study can continue for up to 4 additional patients while waiting for the first 14 patients to be evaluated. Patients will be considered evaluable for response if they are eligible for treatment, and receive 1 dose of therapy. Those patients who are deemed not evaluable will be replaced.

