### 3.2 Secondary Objective & Hypothesis

**Objective:** Determine the biomarkers of response

**Hypothesis:** Pembrolizumab and sEphB4HSA combination induces T and NK cell activation and infiltration into tumor, and induces integrin expression in tumor vessels

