#### **4.2.3.3 Biomarker Research**

Archived tumor tissue will be obtained from all patients entering study, for central PD-1 and PD-L1 immunohistochemical testing by Merck, and will be repeated while on treatment after cycle #2 in order to understand the role that the combination therapy has on the expression levels of these markers. Patients will have research blood collections before initiating the treatment and before infusions on day 1 of every 4th cycle for quantitative peripheral blood T cell subset analysis using flow cytometry, CTCs will be assessed for PD-L1 expression along with analysis of the constituents of circulating tumor cell clusters.

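### Quantitative biomarkers are to be analysed by patient groups with no cut-point fixed; analysing them on their measured scale would keep information that a cohort of at most 25 cannot spare

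*Combined protocol and SAP*

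**What the plan says.** Section 3.2 gives the secondary objective as "Determine the biomarkers of response". Section 8.2 states how this will be done: for ORR, OS and PFS, "each of these will be analyzed in groupings of patients according to biomarkers of interest including" five lettered items. These are PD-L1 on archival tissue and on circulating tumor cells, peripheral T-cell subsets, T-cell infiltration of the tumor, genomic complexity, and integrin pattern in tumor vessels. The list is open-ended.

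Several of these are measured quantities in the protocol's own terms. Section 4.2.3.3 plans "quantitative peripheral blood T cell subset analysis using flow cytometry", and Section 8.2 itself describes the T-cell infiltration as quantitative. Section 4.2.3.2 adds subgroups by pretreatment PD-L1.

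None of these sections gives a cut-point, number of groups, test, significance level or ranking of markers for the biomarker work. The cohort size rests on the primary response test alone: "up to 25 patients are required in each arm to have sufficient power to test the hypothesis". Section 4.2.3 calls the biomarker endpoints descriptive or exploratory, a different status from the one in Section 3.2.

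**The concern.** Turning a measured marker into two or more groups treats all patients on one side of the cut as alike. That costs power in any study, and here there are at most 25 patients per cohort. Section 2.1 records that the lung cohort is closed, and Section 7.1.2.7 allows the biopsy to be omitted when no site is safe, so some markers will have fewer patients.

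Because no cut is fixed, nothing in the plan stops it from being settled after outcomes are known. Five families on three endpoints make at least 15 comparisons per cohort. At stake is the secondary objective: a real marker may be missed, or a chance one reported as a biomarker of response.

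**Working it through.** **The plan's own figure.** Section 8.2 uses a Simon optimal design with rates of 20% and 45%, error probabilities of 0.10, 14 patients in stage 1, 25 in total, and success at 8 or more responses. With X1 ~ Bin(14, p) and X2 ~ Bin(11, p), stopping at 3 or fewer in stage 1, the chance of success is the sum over x = 4 to 14 of P(X1 = x) × P(X2 ≥ 8 − x). This gives 0.0933 at p = 0.20 and 0.9026 at p = 0.45, and a full search returns the same design as optimal. So 25 is the right number for the response test. No figure supports the biomarker analyses.

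**Inputs for the check.** From the plan: n = 25, three endpoints, five lettered families, 8 responders as the minimum for success, and about 11 at the design alternative (0.45 × 25 = 11.25). Assumed, because the plan is silent: a median split (12/13), Fisher's test for response, two-sided 5%, and normally distributed marker values.

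**Power for response** (6,000 simulations; repeat runs differ by one to two points):

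| Responders of 25 | Marker difference | Median split, Fisher | Rank-sum on measured value |
|---|---|---|---|
| 8 | 0.8 SD | 19% | 41% |
| 8 | 1.0 SD | 31% | 58% |
| 8 | 1.2 SD | 43% | 73% |
| 11 | 0.8 SD | 41% | 43% |
| 11 | 1.0 SD | 57% | 61% |
| 11 | 1.2 SD | 72% | 78% |

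At 1 SD, over every responder count from 5 to 12, the rank-sum test is ahead by about 4 to 31 points.

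**Power for PFS and OS.** With uncensored times and a log hazard ratio of 0.4 to 0.8 per SD, a Cox model per SD beats a median-split log-rank test by about 12 to 19 points. For reference, the large-sample efficiency of a median split is 2/π = 0.64.

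**Chance findings.** If k independent tests each have size 0.05, P(at least one false positive) = 1 − 0.95^k.

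- k = 15 (5 × 3): 1 − 0.463 = 53.7%.
- k = 18 (PD-L1 on tissue and on circulating tumor cells counted separately, 6 × 3): 60.3%.
- Fisher's test is conservative. With 8 of 25 responders and a 12/13 split its exact size is 3.0%. Five such tests plus ten at 5% give 1 − 0.970^5 × 0.95^10 = 1 − 0.858 × 0.599 = 48.6%.
- Null simulation at n = 25 (1,500-2,000 replicates, response rate 30%, markers and endpoints from independent to strongly correlated, Fisher or chi-square for response): 47-60% with five markers, 47-68% with six, 60-75% with eight.

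**Cut chosen after the fact.** For one null marker at n = 25, taking the best of all cuts that leave at least 5 patients per group raises the false-positive rate from a nominal 5% to about 15% for response (Fisher) and about 31% for an uncensored log-rank test.

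**The case against.** The plan says only that patients will be grouped. The median split, Fisher's test and the 5% level are assumptions, and grouped response rates and Kaplan-Meier curves could be purely descriptive. Section 4.2.3 calls the biomarker endpoints descriptive or exploratory, and formal error control is not normally expected of such analyses in a phase IIa trial of this size. That stands, and it keeps the point minor. It does not remove it: Section 3.2 makes biomarkers of response the secondary objective, Section 8.2 does not say the results are hypothesis-generating only, and the measured scale is the better choice for exploratory work too.

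The size of the power loss can also be challenged. Eight responders is among the scenarios least kind to grouping, and part of that gap is the discreteness of Fisher's test (actual size 3.0% at 8 responders, 4.7% at 11). At 11 responders the loss for response is about 2 to 6 points. This stands, so the loss must be given as a range.

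A reader might infer that a chance biomarker is more likely than not. The documents do not support that: they set no level and plan no formal tests. Even at 5%, at least 14 independent tests are needed to pass one half (1 − 0.95^13 = 48.7%; 1 − 0.95^14 = 51.2%), and the 15-test figure falls to 48.6% with Fisher's actual size. Nor do the documents show any intention to pick cuts after seeing outcomes; they leave the matter open.

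A reader might also want a marker declared only if it survives false-discovery-rate adjustment. With one true signal among 15 tests the threshold is near 0.05/15 = 0.0033, where rank-sum power at 1 SD and 8 responders is only about 18-19%. It is about 31% if all three of the marker's endpoint tests count (threshold 0.01). That works against finding real markers.

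**Conclusion.** The point holds in this form: the stated method groups quantitative markers, with no cut fixed, in at most 25 patients per cohort, and a measured-scale analysis is better at almost no cost. The gain is about 4 to 31 points of power for response at a 1 SD difference, and about 12 to 19 points for time-to-event outcomes. Both rest on an assumed median split and a two-sided 5% level; the second also assumes uncensored data.

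If 15 comparisons were each tested at 5%, at least one false positive would appear with a chance of roughly 47-60%. It would be higher if sub-markers are counted separately or cuts are chosen after outcomes are seen. That is close to even odds, conditional on formal testing, and not a figure the plan implies by itself. The point is a desirable improvement to the secondary and exploratory analyses and leaves the primary response decision untouched.

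**What to change.** In Section 8.2:

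- Make the main analysis of each quantitative marker use its measured value: a rank-sum test with AUC and confidence interval for response, and a Cox model per SD for PFS and OS.
- Keep groups for display only, and fix the PD-L1 cut before outcomes are examined.
- Report how many marker-by-endpoint comparisons were made and label the results hypothesis-generating. False-discovery-rate adjusted p-values may be shown alongside but should not be a required threshold.
- Reconcile Section 3.2 (secondary objective) with Section 4.2.3 (descriptive or exploratory).

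The cost is SAP wording and minor programming, with no new samples. The downside is that a per-SD effect is slightly harder to read than a group comparison and assumes a roughly log-linear effect.

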## **5.0 METHODOLOGY**

### **5.1 Entry Criteria**

#### **5.1.1 Diagnoses for entry into the trial**

##### **One of the following:**

A) Locally advanced or metastatic non-small cell lung cancer that has progressed after at least 1 line of platinum based chemotherapy.

- Patients may have received up to 2 prior lines of chemotherapy

- Patients with actionable alterations in EGFR/ALK/ROS1/BRAF must also have progressed after treatment with a tyrosine kinase inhibitor appropriate for their genetic alteration.
- Untreated patients who refuse 1st line platinum based chemotherapy are also eligible

Note: As of the July 2018 Interim analysis, the NSCLC carcinoma cohort is closed

B) Squamous Cell Carcinoma of the head and neck whose disease has progressed after at least 1 line of platinum based chemotherapy

- Patients may have received up to 2 prior lines of chemotherapy.
- Untreated patients who refuse 1st line platinum based chemotherapy are also eligible
- Patients who relapse within 6 months of adjuvant cisplatin based concurrent chemo-radiation, or neoadjuvant cisplatin based therapy can be considered eligible without an additional course of platinum chemotherapy for relapsed disease.
- Patients may have either locally recurrent or distant metastatic disease.

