## 6.0 TRIAL FLOW CHART

### 6.1 Study Flow Chart

Trial Period:	Screening Phase		Treatment Cycles a								End of Treatment	Post-Treatment		
	Pre-screening (Visit 1)	Main Study Screening (Visit 2)	1	2	3	4	To be repeated beyond 8 cycles					Safety Follow-up	Survival Follow-Up	
Treatment Cycle/Title:							5	6	7	8				
Scheduling Window (Days):		-28 to -1		± 3	± 3	± 3	± 3	± 3	± 3	± 3	At time of Discon	30 days post discon	Every 12 weeks	
Administrative Procedures														
Pre-screening Consent	X													
Informed Consent		X												
Inclusion/Exclusion Criteria		X												
Demographics and Medical History	X													
Prior and Concomitant Medication Review	X													
Trial Treatment Administration			X	X	X	X	X	X	X	X				
Post-study anticancer therapy status												X	X	
Survival Status						X					X	X	X	X
Clinical Procedures/Assessments														
Review Adverse Events	X	X	X	X	X	X	X	X	X	X	X	X	X	X
Full Physical Examination		X												
Directed Physical Examination	X		X	X	X	X	X	X	X	X				
Vital Signs and Weight	X	X	X	X	X	X	X	X	X	X				
ECOG Performance Status	X	X	X	X	X	X	X	X	X	X				
Laboratory Procedures/Assessments: analysis performed by LOCAL laboratory														
Pregnancy Test – Urine or Serum β-HCG 	X	X	X	X	X	X	X	X	X	X				
PT/INR and aPTT		X				X					X			
CBC with Differential		X	X	X	X	X	X	X	X	X				

Trial Period:	Screening Phase		Treatment Cycles a							End of Treatment	Post-Treatment		
	Pre-screening (Visit 1)	Main Study Screening (Visit 2)	1	2	3	4	To be repeated beyond 8 cycles				Discon	Safety Follow-up	Survival Follow-Up
Treatment Cycle/Title:							5	6	7	8			
Scheduling Window (Days):		-28 to -1		± 3	± 3	± 3	± 3	± 3	± 3	± 3	At time of Discon	30 days post discon	Every 12 weeks
Comprehensive Serum Chemistry Panel		X	X	X	X	X	X	X	X	X			
Urinalysis		X				X				X			
T3, FT4 and TSH		X				X				X			
Efficacy Measurements													
Tumor Imaging			X		X		X		X		X		
Tumor Biopsies/Archival Tissue Collection/Correlative Studies Blood													
Archival or Newly Obtained Tissue Collection			X			X							
Exploratory Biomarker Blood Collection			X				X				X	X	
Anti-Drug Antibodies and Serum Banking			X	X	X						X		

a only in women of child bearing potential

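### Where archival baseline tissue predates earlier therapy, the paired biomarker change in Section 8.2 cannot be attributed to study treatment; vessel integrin is not in that comparison

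*Combined protocol and SAP*

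**What the plan says.** Section 8.2 states the before/after analysis in one sentence. As the measure of treatment's impact it lists PD-L1 levels and T-cell subsets, and it ends: "Tumor infiltrating lymphocytes will be compared in archival and post treatment biopsy specimens". Section 4.2.3.3 describes the same pair of specimens. At entry, "Archived tumor tissue will be obtained from all patients entering study", and the testing "will be repeated while on treatment after cycle #2 in order to understand the role that the combination therapy has" on these markers. The only new biopsy that the inclusion criteria require is the one after two cycles. The flow chart row is labelled "Archival or Newly Obtained Tissue Collection", so a fresh baseline sample is allowed but not required.

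On prior treatment, Section 5.1.1 takes patients who have progressed after platinum and adds that "Patients may have received up to 2 prior lines of chemotherapy". In the head and neck cohort, early relapse after cisplatin-based chemoradiation also qualifies. Untreated patients who decline platinum are eligible too.

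The hypothesis in Section 3.2 is that the "Pembrolizumab and sEphB4HSA combination induces T and NK cell activation and infiltration into tumor, and induces integrin expression in tumor vessels". Section 4.2.3 calls the biomarker endpoints descriptive or exploratory.

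**The concern.** A before/after comparison isolates the study period only if the first sample is taken at its start. An archival block may have been taken before platinum, before a second chemotherapy line or before chemoradiation, and from a different lesion. PD-L1 and lymphocyte infiltration may have changed by the time of cycle 1, and the planned comparison would carry that change along with any effect of the study drugs.

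The marker list also falls short of the hypothesis. Integrin expression in tumor vessels enters Section 8.2 only as a factor for grouping response, PFS and OS, so its induction is never compared before and after. NK cells appear in Sections 3.1, 3.2 and 8.1, but Section 8.2 names no NK measure.

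At stake is the trial's account of mechanism: whether a reported rise in infiltration can be described as something that the treatment did.

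**Working it through.** **1. The plan's own figure.** The documents give no sample size for the biomarker comparison. The only one is for response rate: 14 then 25 patients per cohort, positive at 8 or more, 20% against 45%. With X ~ Bin(14, p), Y ~ Bin(11, p) and stopping at 3 or fewer, P(positive) = Σ over x = 4 to 14 of P(X = x) · P(Y ≥ 8 − x). This gives 0.0933 at p = 0.20 and 0.9026 at p = 0.45. The expected size under 20% is 14 + (1 − 0.6982) × 11 = 17.3. An exact search returns this as the optimal design at 0.10/0.10. So 25 reproduces, and nothing below alters it.

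**2. What the paired difference contains.** For one patient, write

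D = (on-treatment − archival) = T + P + S

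- T is the change from cycle 1 to the on-treatment biopsy.
- P is the change from the archival date to cycle 1, including any effect of intervening therapy.
- S is the difference between the two sampled sites.

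The plan observes only D. Checking each term against the text:

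- **P.** No section limits the age of the block or requires it to follow the last therapy. Section 5.1.1 makes intervening platinum or chemoradiation likely for many patients. Exclusion criterion 6 lets chemotherapy or radiation end as little as two weeks before Day 1. No adjustment or stratification is planned.
- **S.** Section 7.1.2.7 leaves the biopsy site to the investigator on safety grounds and does not match it to the archival site.
- **T.** Section 5.2.3 confirms a single arm, so even a clean T is the effect of both drugs together and cannot be split from pembrolizumab's own effect.

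P and S cannot be estimated from the documents, which give neither sample dates nor sites.

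**3. How much a drift could matter (illustration only).** Section 8.2 names no test. Assume a two-sided 5% paired t-test, T = 0, and a mean of P + S equal to d standard deviations of the paired differences. The chance of a positive result is P(|t′| > t(0.975, n − 1)), where t′ is noncentral t with n − 1 degrees of freedom and noncentrality d√n. For n = 25 and d = 0.3, the noncentrality is 0.3 × 5 = 1.5.

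| Assumed d | 14 pairs | 25 pairs |
|---|---|---|
| 0.2 | 11% | 16% |
| 0.3 | 18% | 30% |
| 0.5 | 41% | 67% |
| 0.8 | 79% | 97% |

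With d = 0 the rate is 5%. Both columns assume that every patient yields a pair. More pairs make the problem worse, because the test becomes more certain of a difference that is not T.

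**4. Markers, hypothesis against analysis.**

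- T-cell infiltration: covered by T-cell subsets and infiltrating lymphocytes.
- NK infiltration: possibly inside infiltrating lymphocytes, but not separately identified.
- Vessel integrin: absent from the before/after list and present only as grouping factor (e).

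**5. T-cell subsets.** Section 4.2.3.3 draws blood for flow cytometry before treatment and on day 1 of every fourth cycle. That baseline follows prior therapy by construction, yet Section 8.2 places the before/after comparison of subsets in tissue only.

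**The case against.** The best defence is that this is exploratory work. The objective in Section 3.2 is to find biomarkers of response, which Section 8.2 addresses by grouping outcomes; the mechanism statement is only its hypothesis. No biomarker test, threshold or success rule is set, so nothing is formally declared. Some archival blocks may come from a post-platinum relapse, some patients will be untreated, and the flow chart permits fresh baseline tissue. This all stands and lowers the weight of the point, but Section 8.2 still labels the contrast as the impact of treatment and does not tell clean pairs from the others.

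Several stronger readings are tempting and are not supported:

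- **That prior-therapy effects will be credited to the combination in most patients.** Without sample dates, one can say only that they cannot be separated where the block is older.
- **That NK cells are left out.** They are lymphocytes and may be counted among the infiltrating cells. What is missing is a named NK measure.
- **That measuring T-cell subsets in tissue is an error.** Section 4.1 discusses CD8+ and FoxP3+ cells in tumor, so tissue subsets are legitimate. Blood is an additional, cleaner comparison.
- **That the flow chart puts the second tissue sample at cycle 4, against cycle 2 in the text, with a large loss of pairs.** The table was extracted from PDF. Moved one column left, the antibody, biomarker-blood and imaging rows agree with Sections 4.2.3.3, 7.1.2.6 and 7.1.2.7, and tissue falls at screening and cycle 3, that is, after two cycles. Section 5.6 also does not require stopping at a first unconfirmed progression. Pairs will be lost where no site is safe to biopsy, but the number is unknown.

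**Conclusion.** The point holds as a cheap improvement to a secondary or exploratory analysis. Following Section 8.2 as written mixes change since the archival sample with change on study treatment wherever the block predates prior therapy or comes from another site. The bias has no computable size or direction; the percentages above rest on an assumed drift, an assumed test and complete pairs. The absence of vessel integrin from the before/after comparison is unambiguous, while the NK gap is one of specification. The primary response-rate test is untouched. The NSCLC cohort is closed, so prospective changes concern the head and neck cohort, but tissue already held from either cohort can still be classified.

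**What to change.** In Section 8.2:

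(a) Record the date and site of the baseline tissue and any anticancer therapy given between it and cycle 1. Use the most recent available block.

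(b) Attribute paired change to study treatment only where the baseline tissue was taken after the last prior therapy. Report the remaining pairs as change since archival sample. State that, without a control arm, the combination's effect cannot be separated from that of pembrolizumab alone. Identify pairs taken from different sites.

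(c) Add vessel integrin to the paired comparison, and NK cells with a named marker where tissue allows.

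(d) Also compare T-cell subsets between the pre-treatment and on-treatment blood already drawn.

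The cost is SAP wording, CRF fields for tissue date and site (Section 7.1.1.5.2 already has prior cancer treatments reviewed), and stains on tissue already collected if enough remains. No extra biopsy is needed. The downside is that fewer pairs support the attribution, so that estimate is less precise.

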### 2.1 Trial Design

An open label, single arm, phase IIa clinical trial of the combination of pembrolizumab with sEphB4-HSA in 2 parallel cohorts of patients with either advanced /metastatic non-small cell lung cancer (NSCLC) or relapsed/metastatic squamous cell carcinoma of the head and neck (SCCHN).

Note: As of the July 2018 Interim analysis, the NSCLC carcinoma cohort is closed

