### 2.2 Trial Diagram

#### Phase IIa

## 3.0 OBJECTIVES & HYPOTHESES

### 3.1 Primary Objective & Hypothesis

**Objective:** Determine the response rate of the combination of pembrolizumab and sEphB4-HSA as combination therapy

**Hypothesis:** combination of pembrolizumab and sEphB4-HSA will be more active than historical data on single agent pembrolizumab by activating T cell and promoting T cell NK cell trafficking into the tumor respectively

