## 4.2 Rationale

### 4.2.1 Rationale for the Trial and Selected Subject Population

Pembrolizumab is active in SCCHN and NSCLC. In the Keynote-12 trial of 132 patients with recurrent or metastatic SCCHN the overall response rate was 25%. In the Keynote-001 trial of NSCLC patients, the overall response rate was 19%, though in patients who had high expression of PD-L1, the response rate was 45%. sEphB4-HSA also has activity in head neck cancer around 10% and has a limited experience in NSCLC, however, the in vitro and in vivo effects on immune cell infiltration into tumors suggests a potential for synergy of the combination. Both drugs have different mechanism of action and no overlapping toxicity. The current outcomes of patients with relapsed/metastatic disease with either histology are unsatisfactory. Combination of the drugs may thus be more active than each one alone without increase in toxicity. Both tumor types are incorporated into a single clinical trial to improve the opportunity to observe toxicities that may be unique to the combination in a larger number of patients.

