#### **4.2.3.2 Efficacy Endpoints**

Overall response rate is the primary efficacy endpoint. In the Keynote-001 clinical trial, the overall response rate in previously treated patients was 19%, while the response rate in the PD-L1 positive population was 45%. We expect that the response rate for the combination of sEphB4-HSA will be higher than 20% in patients who are not pre-selected for PD-L1 positivity and approach 45% for the 2 drug combination in patients with no prior selection for PD-L1. Progression free survival, overall survival and duration of response will be secondary efficacy endpoints. All efficacy endpoints will be analyzed for each whole cohort as well as subgroups depending on pretreatment PD-L1 expression.

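### Head and neck cohort: 8 of 25 responses tests a 20% rate but is read as a signal of benefit over either drug alone, although the protocol puts pembrolizumab alone at 25%

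*Combined protocol and SAP*

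**What the plan says.** Section 8.2 sizes each cohort separately with a Simon optimal two-stage design: null 20%, alternative 45%, α = β = 0.10, 14 patients at the interim, 25 in total, success at 8 or more responses. One pair of rates serves both diseases; π is "the true response rate (same rate used for NSCLC and H&N Cancer").

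Success is given two readings. The first is that the true rate exceeds 20% and is compatible with 45%. The second is that the result is a signal that the "two drugs together are better than either alone". Section 8.2 also says that "Best overall response at any time will be compared in the study population to benchmark values in the literature", without giving a value or a decision rule.

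The single-agent rates are elsewhere in the protocol:

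- Section 3.1 sets the hypothesis: "combination of pembrolizumab and sEphB4-HSA will be more active than historical data on single agent pembrolizumab".
- Section 4.2.1, pembrolizumab in head and neck cancer: "In the Keynote-12 trial of 132 patients with recurrent or metastatic SCCHN the overall response rate was 25" per cent.
- Section 4.2.1, the other agent: "sEphB4-HSA also has activity in head neck cancer around 10" per cent.
- Section 4.2.3.2, where the 20% and 45% are motivated, cites only lung cancer data: "In the Keynote-001 clinical trial, the overall response rate in previously treated patients was 19" per cent overall, and 45% in PD-L1 positive patients.

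Section 2.1 adds: "As of the July 2018 Interim analysis, the NSCLC carcinoma cohort is closed".

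**The concern.** A claim that the pair beats either drug alone has to clear the better of the two single-agent rates. In SCCHN the protocol's own figures are 25% and about 10%, so the bar is 25%. The test is set at 20%, a rate that the protocol supports only with lung cancer data. A result can therefore reject 20% and still say little about 25%.

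The stated 10% error belongs to the 20% null. A reader who meets the comparative sentence directly after the cut-off will naturally carry the 10% over to it. What is at stake is how often a combination with no added benefit in SCCHN would be reported as a signal of added benefit. With the lung cohort closed, SCCHN is the only cohort in which the sentence can still be used, and it is the one where it does not fit.

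**Working it through.** **Inputs.** From Section 8.2: n₁ = 14, n = 25, success at 8 or more, null 20%, alternative 45%. From Section 4.2.1: pembrolizumab alone in SCCHN 25% (132 patients); sEphB4-HSA alone about 10%; pembrolizumab alone in lung cancer 19%.

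**Interim rule.** Section 8.2 closes an arm at fewer than 3 responses of 14 and continues at 4 or more. Exactly 3 is not assigned. The Simon optimal design named there stops at 3 or fewer. Both readings are shown.

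**Formula.** With X₁ ~ Bin(14, p) and X₂ ~ Bin(11, p), and stopping when X₁ ≤ r₁,

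P(success | p) = Σ P(X₁ = x) · P(X₂ ≥ 8 − x), summed over x = r₁ + 1 to 14.

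**Step 1: reproduce the plan.** A full search for 20% versus 45% with α ≤ 0.10 and power ≥ 0.90 returns stop at 3 or fewer of 14 and success at 8 or more of 25, with α = 0.0933 and power = 0.9026. The design is what the protocol says it is.

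**Step 2: put in p = 0.25, stopping at 3 or fewer.**

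| x of 14 | P(X₁ = x) | P(X₂ ≥ 8 − x) | Product |
|---|---|---|---|
| 4 | 0.2202 | 0.2867 | 0.0631 |
| 5 | 0.1468 | 0.5448 | 0.0800 |
| 6 | 0.0734 | 0.8029 | 0.0589 |
| 7 | 0.0280 | 0.9578 | 0.0268 |
| 8 or more | 0.0103 | 1 | 0.0103 |

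The products sum to 0.239. If exactly 3 of 14 continues, add P(X₁ = 3) · P(X₂ ≥ 5) = 0.2402 × 0.1146 = 0.0275, giving 0.267.

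**Step 3: success probability across true rates.**

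| True rate | Stop at ≤ 3 of 14 | 3 of 14 continues |
|---|---|---|
| 18% | 5.6% | 6.4% |
| 19% (lung reference) | 7.3% | 8.3% |
| 20% | 9.3% | 10.6% |
| 25% (SCCHN reference) | 23.9% | 26.7% |
| 30% | 43.8% | 47.8% |
| 33% | 56.1% | 60.6% |
| 45% | 90.3% | 93.1% |

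The success probability reaches 10% at a true rate of 20.3% (19.8% if 3 continues). A 10% error therefore covers the lung reference of 19% but not the SCCHN reference of 25%.

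**Step 4: uncertainty in the 25%.** The documents give no numerator. Assuming 33 of 132, the exact (Clopper-Pearson) 95% interval is 17.9% to 33.3%. Rows 18% to 33% above cover that range: 5.6% to 56.1%.

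**Step 5: the smallest qualifying result.** 8/25 = 32%, with an exact 95% interval of 14.9% to 53.5%, ignoring the interim look. It contains 25%.

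**The case against.** - **The wording is modest.** The plan calls the result a signal, in a single-arm phase IIa trial with no control, and attaches α only to the 20% null. That is fair, and the comparison is not presented as confirmatory. But the sentence is still comparative and a numeric rule triggers it. A signal rule also has a false-signal rate, and here it is not the one a reader would assume.
- **The 25% is one outside estimate.** Its assumed interval contains 20%, and the protocol does not show that its population matches this one: Section 5.1.1 also admits untreated patients who refuse platinum. This stands as a limit on the 24% figure, which is conditional on 25% and could be much lower or much higher. It does not rescue the comparative reading, because an uncertain reference is no reason to treat rejection of 20% as evidence of added benefit.
- **The literature comparison covers it.** A reader could set 25% beside the result, which helps. With no named value and no rule, it does not restrain the 8-of-25 conclusion.
- **The test of 20% is itself conditional.** This stands. α is 9.3% only if 3 of 14 stops the arm; otherwise it is 10.6%, slightly above the stated 0.10.
- **Meeting the rule needs an observed 32%, above 25%.** True, but Step 5 shows how little 8 of 25 says about the difference.

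**Conclusion.** The concern holds. The two-stage design is sound as a test of 20%, provided 3 of 14 stops the arm. The comparative conclusion attached to it does not follow for SCCHN, because the protocol's own reference for pembrolizumab alone in that disease is 25%. If the true combination rate is 25%, the rule is met 23.9% of the time (26.7% if 3 of 14 continues), against a stated error of 10% that applies to a different null.

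The mismatch between sections needs no assumption. The size rests on taking 25% as the reference; over 18% to 33% it runs from 5.6% to 56.1% (6.4% to 60.6% if 3 continues). This should be fixed. It changes what the trial may conclude in its only open cohort, not how the trial is run.

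**What to change.** Keep n = 25 and 8 of 25 as the test of 20%. For SCCHN, replace the comparative clause in Section 8.2 with text such as:

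> For SCCHN, 8 or more responses will be reported as a response rate above 20%, not as superiority to pembrolizumab alone, for which the reference rate is 25% (Section 4.2.1). If the true rate is 25%, this rule is met 23.9% of the time (26.7% if accrual continues after 3 of 14). The observed response rate will be reported with its exact 95% confidence interval beside 25%.

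Once the outcome at exactly 3 of 14 is specified, only the matching figure need stay. A short note that the 25% is an estimate from a population that may differ would also help.

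**Cost.** One clause, one disclosed operating characteristic, and a less favourable statement at 8 or more responses. The test, cut-off, power and number of patients are unchanged.

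**Option, not required.** A higher cut-off for the comparative statement only (figures with stopping at 3 or fewer of 14):

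| Cut-off | Success at 25% | Power at 45% |
|---|---|---|
| 9 of 25 | 14.0% | 84.6% |
| 10 of 25 | 6.9% | 74.9% |

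Both fall below the planned 90% power, by about 6 and 15 points from the present 90.3%. Either needs a protocol amendment and would move a threshold during an open-label trial; the documents do not say whether the SCCHN interim has taken place. A full redesign for 25% versus 45% at α = β = 0.10 would need 44 patients (Simon optimal) or 39 (minimax) and is not proposed.
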